7.14 Trial Blinding/Masking

This is an open-label pilot trial; therefore, the Sponsor, investigator and subject will know the treatment administered.

7.15 Randomization or Treatment Allocation

N/A

7.16 Stratification

N/A

7.17 Concomitant Medications/Vaccinations (allowed & prohibited)

Medications or vaccinations specifically prohibited in the exclusion criteria are not allowed during the ongoing trial. If there is a clinical indication for one of these or other medications or vaccinations specifically prohibited during the trial, discontinuation from trial therapy or vaccination may be required. The investigator should discuss any questions regarding this with the Merck Clinical team. The final decision on any supportive therapy or vaccination rests with the investigator and/or the subject's primary physician.

7.17.1 Acceptable Concomitant Medications

All treatments that the investigator considers necessary for a subject's welfare may be administered at the discretion of the investigator in keeping with the community standards of

medical care. All concomitant medication will be recorded in Epic including all prescription, over-the-counter (OTC), herbal supplements, and IV medications and fluids.

All concomitant medications received within 28 days before the first dose of trial treatment and 30 days after the last dose of trial treatment should be recorded. Concomitant medications administered after 30 days after the last dose of trial treatment should be recorded for SAEs and ECIs.

7.17.2 Prohibited Concomitant Medications and Therapies

Subjects are prohibited from receiving the following therapies during the Screening and Treatment Phase (including retreatment for post-complete response relapse) of this trial:

- Antineoplastic systemic chemotherapy or biological therapy not specified in this protocol
- Immunotherapy not specified in this protocol
- Chemotherapy not specified in this protocol
- Live vaccines within 30 days prior to the first dose of trial treatment and while participating in the trial. Examples of live vaccines include, but are not limited to, the following: measles, mumps, rubella, varicella/zoster, yellow fever, rabies, BCG, and typhoid vaccine.
- All herbal and natural supplements that are being used will be recorded at all clinic visits. Natural therapies and herbal supplements may stimulate or suppress subject's immune system. Immune suppressants may reduce the efficacy of pembrolizumab and their concomitant use may potentially increase the risk of infections. Concomitant use of immune stimulants may potentially increase the risk of adverse auto-immune responses. Concomitant use of the natural therapies and herbal supplements in Table 8 below are prohibited
- Emerging data suggests that marijuana can affect response rates. The use of marijuana and marijuana derived products are allowed in this study. Subjects will be made aware (in the consent form) of the potential risks of using marijuana while on the study.

Table 8 Prohibited Concomitant Natural Therapies and Herbal Supplements

Name of herbal supplement	
Immune stimulating agents	
1. Coriolus Mushroom DHEA	16. Pokeweed
2. 7-keto-DHEA	17. Pycnogenol
3. Echinacea*	18. Coriolus Mushroom
4. European mandrake	19. DHEA
5. European mistletoe	20. 7-keto-DHEA
6. Fo-Ti Root	21. European mandrake
7. Ginseng, panax and siberian	22. Quillaia
8. Glossy Privet (ligustrum)	23. Reishi Mushroom (gandoderma)
9. Greater Celandine	24. Shitake Mushroom
10. Jiaogulan	25. Sweet Annie
11. Larch Arabinogalactan	26. Terminalia chebula
12. Lycium	27. Thunder god vine
13. Melatonin	28. Wild indigo
14. MGN-3	29. Zinc
15. Podophyllum	Note: *Can be immune suppressing also

Immune suppressing agents	
1. Bitter Melon	8. Fish Oils
2. Caramel Color	9. Licorice
3. Carrageenan(intravenous only)	10. Periwinkle(vinca)
4. Echinacea**	11. Poria Mushroom
5. Indole-3-carbinol	Note : ** Can be immune stimulating also
6. Ipriflavone	
7. Hydrazine	

Subjects who, in the assessment by the investigator, require the use of any of the aforementioned treatments for clinical management should be removed from the trial. Subjects may receive other medications that the investigator deems to be medically necessary.

The Exclusion Criteria describes other medications which are prohibited in this trial. There are no prohibited therapies during the Post-Treatment Follow-up Phase.

7.18 Pharmacokinetic/Pharmacodynamic Evaluations

NA

7.19 Blood Collection for Anti-Pembrolizumab Antibodies

NA

7.20 Blinding/Unblinding

N/A

7.21 Diet/Activity/Other Considerations

Subjects should maintain a normal diet unless modifications are required to manage an AE such as diarrhea, nausea or vomiting.

7.22 Contraception

Both pembrolizumab and ferumoxytol may have adverse effects on a fetus in utero. Furthermore, it is not known if pembrolizumab has transient adverse effects on the composition of sperm. Non-pregnant, non-breast-feeding women may be enrolled if they are willing to use 2 methods of birth control or are considered highly unlikely to conceive. Highly unlikely to conceive is defined as 1) surgically sterilized, or 2) postmenopausal (a woman who is ≥ 45 years of age and has not had menses for greater than 1 year without alternate medical causes will be considered postmenopausal), or 3) not heterosexually active for the duration of the study. In women ≤ 45 years of age a high follicular stimulating hormone (FSH) level in the post-menopausal range may be used to confirm post menopausal state in women not using hormonal contraception or hormonal replacement therapy. The two birth control methods can be either two barrier methods or a barrier method plus a hormonal method to prevent pregnancy. Subjects should start using birth control from study Visit 1 throughout the study period up to 120 days after the last dose of study therapy. Male subjects should agree to use an adequate method of contraception, including but not limited to, abstinence from heterosexual activity, starting with the first dose of study therapy through 120 days after the last dose of study therapy.

The following are considered adequate barrier methods of contraception: diaphragm, condom (by the partner), copper intrauterine device, sponge, or spermicide. Appropriate hormonal contraceptives will include any registered and marketed contraceptive agent that contains an estrogen and/or a progestational agent (including oral, subcutaneous, intrauterine, or intramuscular agents).

Subjects should be informed that taking the study medication may involve unknown risks to the fetus (unborn baby) if pregnancy were to occur during the study. In order to participate in the study they must adhere to the contraception requirement (described above) from study Visit 1 throughout the study period up to 120 days after the last dose of study therapy. If there is any question that a subject will not reliably comply with the requirements for contraception, that subject should not be entered into the study.

7.23 Use in Pregnancy

If a subject inadvertently becomes pregnant while on treatment with pembrolizumab or ferumoxytol, the subject will immediately be removed from the study. The site will contact the subject at least monthly and document the subject's status until the pregnancy has been completed or terminated. The outcome of the pregnancy will be reported to the Sponsor and to Merck without delay and within 24 hours to the Sponsor and within 2 working days to Merck if the outcome is a serious adverse experience (e.g., death, abortion, congenital anomaly, or other disabling or life-threatening complication to the mother or newborn).

The study investigator will make every effort to obtain permission to follow the outcome of the pregnancy and report the condition of the fetus or newborn to the Sponsor. If a male subject impregnates his female partner, the study personnel at the site must be informed immediately and the pregnancy reported to the Sponsor and to Merck.

7.24 Use in Nursing Women

It is unknown whether pembrolizumab or ferumoxytol is excreted in human milk. Since many drugs are excreted in human milk, and because of the potential for serious adverse reactions in the nursing infant, subjects who are breast-feeding are not eligible for enrollment.

8.0 RESPONSE ASSESSMENT, IMAGE PROCESSING AND BIOMARKERS

8.1 Definitions for Response assessment:

The study will use the following criteria for the assessment of brain lesions.

Complete response (CR): Complete disappearance of all enhancing abnormalities on clinical enhanced MRI scan (in the absence of gadolinium, ferumoxytol enhancement will be used). Some subjects will have a small but persistent enhancing abnormality on MRI related to biopsy or focal hemorrhage. It is often difficult to ascertain whether this represents a residual nidus of tumor or scar tissue. Adjunctive radiologic studies such as SPECT or PET as clinically indicated may be helpful, but often the nature of these abnormalities may only be determined by following the subject with serial scans. If this type of abnormality does not change or slowly involutes over time off therapy and corticosteroids, it is reasonable to categorize it as a CR.

Partial Response (PR): At least 50% decrease in the contrast enhancing lesion seen on MRI as compared to baseline imaging. In the event of multiple lesions, the determination of partial response will be based on the sum of the bi-dimensional measurements (greatest diameter x greatest perpendicular) across lesions AND no new sites of disease

Stable disease (SD): less than a PR but is not progressive disease.

Progressive disease (PD):

- **Suspected Radiographic Progression:** progression will be defined by a 20% increase in volume of enhancement compared to the best response on clinical standard of care MRI. At any time point if progression is suspected on the clinical scan, additional steady state ferumoxytol MRI will be performed within 7 days of the clinical scan. Progression will then be confirmed with a follow up scan in 4 weeks \pm 5 days with a clinical standard of care MRI scan and additional ferumoxytol scan.
- **Persistent Radiographic Progression:** sustained and evident progression greater than increase in volume of enhancement compared to best response on a follow up scan at least 4 weeks after the scan where progression was suspected as per RANO BM form arm 1 or RANO criteria for subjects in arm 2. In cases with persistent radiographic progression the date of initial scan when progression was suspected will be considered to be the date of progression.
- Appearance of any new lesion or site of disease in the brain during or at the end of therapy.
- **Confirmation of true progression:** For the purpose of this study, Histopathologic evidence of viable tumor cells in patients with persistent radiographic progression will be define to have confirmed true progression. True progression is confirmed by histopathology, Pembrolizumab will be stopped and patient swill be taken off-study.. Patients who refuse biopsy or biopsy is not deemed clinically necessary will be taken off study at persistent radiographic progression. However, they will be continued to be monitored with clinical MRI scan and until death.
- **Pseudoprogression (PsP):** for the purpose of this pilot study, PsP may be confirmed by imaging or by pathology.
 - PsP Imaging: stable or decrease in volume of enhancement at 4 weeks (\pm 5 days) after suspected radiographic progression.
 - PsP pathology: No viable tumor tissue is seen by histopathology evaluation on tissue obtained after confirmed radiographic progression by imaging.
- **Clinical progression:** Subjects may be removed from study if they experience symptomatic deterioration without radiographic evidence of disease progression.

Not evaluable (NE): Only relevant if any of the target lesions had additional interventions for clinical managements, patient is unable to get follow up scans or images are of poor quality.

Duration of Best Response: The duration of best response is measured from the time measurement criteria are met for SD, CR or PR (whichever is first recorded) until the first date that recurrent or PD is objectively documented (taking as reference for PD the smallest measurements recorded since the treatment started).

Progression free survival and overall survival will be calculated from the date of diagnosis to the date of confirmed progression or death, respectively. The date of diagnosis was used because the time between the date of diagnosis and the start of treatment or date of enrollment may vary due to subject variables or logistical issues based on radiation planning.

Systemic Lesions (only for Arm 1):

Measurements based on RECIST version 1.1 will be used to make a diagnosis of suspected systemic progression; it will be confirmed using irRC at follow-up.

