5.4.2 Discontinuation of Study Therapy after CR

Discontinuation of treatment may be considered for subjects who have attained a confirmed CR in the brain, and have been treated for at least 24 months with pembrolizumab.

At the discretion of the investigator, subjects who have discontinued therapy after 24 months and have attained and maintained a CR in the brain, but develop progressive systemic disease may be eligible for up to one year of additional treatment with pembrolizumab via the Second Course Phase, if no additional cancer treatment was administered since the last dose of pembrolizumab, the subject meets the safety parameters listed in the Inclusion/Exclusion criteria, and the trial is open. Subjects will resume therapy at the same dose and schedule at the time of initial discontinuation. Additional details are provided in Section 7.9.

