7.11 Second Course Phase (Retreatment Period)

Subjects who stop pembrolizumab with CR in the brain and systemically may be eligible for up to one year of additional pembrolizumab therapy if they progress systemically, but maintain a CR in the brain. This retreatment is termed the Second Course Phase of this study and is only available if the study remains open and the subject meets the following conditions:

Either

- Stopped initial treatment with pembrolizumab after attaining an investigator-determined confirmed CR, and
 - Was treated for at least 24 weeks with pembrolizumab before discontinuing therapy
 - Received at least two treatments with pembrolizumab beyond the date when the initial CR was declared

OR

- Had CR in the brain and systemically and stopped pembrolizumab treatment after 24 months of study therapy for reasons other than disease progression or intolerability

AND

- Experienced an investigator-determined confirmed radiographic disease progression after stopping their initial treatment with pembrolizumab
- Did not receive any anti-cancer treatment since the last dose of pembrolizumab
- Has a performance status of 0 or 1 on the ECOG Performance Scale
- Demonstrates adequate organ function as detailed in Section 5.2
- Female subject of childbearing potential should have a negative serum or urine pregnancy test within 72 hours prior to receiving retreatment with study medication.
- Female subject of childbearing potential should be willing to use 2 methods of birth control or be surgically sterile, or abstain from heterosexual activity for the course of the study through 120 days after the last dose of study medication. Subjects of child bearing potential are those who have not been surgically sterilized or have been free from menses for > 1 year.
- Male subject should agree to use an adequate method of contraception including but not limited to abstinence from heterosexual activity starting with the first dose of study therapy through 120 days after the last dose of study therapy.
- Does not have a history or current evidence of any condition, therapy, or laboratory abnormality that might interfere with the subject's participation for the full duration of the trial or is not in the best interest of the subject to participate, in the opinion of the treating investigator.

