10.0 STATISTICAL ANALYSIS PLAN

Given the exploratory nature of this study, the statistical analyses will be descriptive in nature. For the primary and secondary objectives, sensitivity, specificity, rate of adverse event and distribution of best responses will be analyzed using proportions and exact 95% confidence intervals. Progression free survival and overall survival will be assessed using the Kaplan-Meier product limit estimates. Outcomes in the exploratory objectives will be summarized using descriptive statistics as appropriate; and associations between immunological parameters, PDL-1 expression, clinical responses, radiological responses and other variables will be explored using two sample tests or correlation measures, as appropriate.

Power and sample size calculation for Arm 1

The accrual to arm 1 is stopped with 2 patients. These 2 patients will be described separately and no further analysis will be done.

Power and sample size calculation for Arm 2

For arm 2, we will enroll 43 GBM patients. Here we roughly estimate the precision of sensitivity and specificity in the primary objective based on these 43 patients.

In subjects with GBM, we anticipate to have only one lesion/subject. We assume that all subjects will eventually have disease progression and due to dropout and inoperable cases, a total of $n = 32$ subjects will undergo surgery to provide histopathological data on disease progression. Further, we assume that 40% of the $n = 43$ subjects will develop pseudo-progression and be observed based on follow-up scan.

For sensitivity, further assume that out of the $n = 32$ subjects who will undergo surgery, 26 subjects will have true progression based on pathology (gold standard). Then based on $n = 26$,

if we observe 22 subjects (lesions) for whom the true progression is correctly identified by Ferumoxytol MRI, then the sensitivity will be 85% with a 95% CI between 65% and 96% (Table XX).

Number of subjects (lesions) with true progression	Number of subjects (lesions) whose true progression was detected by Ferumoxytol MRI	Sensitivity	Exact 95% CI of Sensitivity
26	26	100%	87% to 100%
26	24	92%	75% to 99.1%
26	22	85%	65% to 96%
26	20	77%	56% to 91%
26	18	69%	48% to 86%
26	16	62%	41% to 80%

Table 12: Estimated sensitivity and 95% CI based on 26 subjects (lesions).

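### Section 8.1 lets a single scan count as CR or PR and never defines the confirmed CR that Sections 5.4.2 and 7.11 rely on, so the best-response distribution may be overstated by an unknown amount

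*Combined protocol and SAP*

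**What the plan says.** Section 8.1 defines complete response as "Complete disappearance of all enhancing abnormalities on clinical enhanced MRI scan" and partial response as "At least 50% decrease in the contrast enhancing lesion seen on MRI as compared to baseline imaging". Neither definition asks for a second scan or a minimum duration. Serial scans come into CR only for a small residual abnormality after biopsy or haemorrhage: if it stays unchanged or slowly involutes "over time off therapy and corticosteroids, it is reasonable to categorize it as a CR".

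Progression by volume is treated differently in the same section: "Progression will then be confirmed with a follow up scan in 4 weeks". RANO is invoked in 8.1 only for persistent progression in Arm 2, so no confirmation rule for response comes in by that route.

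Two other sections presuppose confirmation. Section 5.4.2 concerns "subjects who have attained a confirmed CR in the brain". The first route in Section 7.11 applies to subjects who stopped "after attaining an investigator-determined confirmed CR", and it also mentions the date on which the initial CR was declared, so it treats initial and confirmed CR as different things. No section says how a CR is confirmed.

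Clinical response and duration of best response form part of secondary objective 2 (Section 3.2), where the pilot data are said to be intended for powering a larger study. In Section 10.0 the "distribution of best responses will be analyzed using proportions and exact 95% confidence intervals".

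**The concern.** A subject who meets a response criterion on any one of several scans has several chances to be counted on the strength of measurement error or a passing change. With no control arm, nothing offsets the resulting upward shift, and the exact interval does not reflect it.

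The protocol itself names sources of low readings. Section 4.0 says that bevacizumab, allowed for up to 3 doses, and corticosteroids can reduce enhancement without a true response. Section 8.1 lets ferumoxytol enhancement stand in for gadolinium, and Section 7.6 allows a non-contrast clinical MRI in some enrolled subjects. An inflated response rate could carry forward into the planning of the larger study. The undefined confirmed CR also leaves readers of 5.4.2 and 7.11 without a common meaning.

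**Working it through.** **The plan's own figures.** The documents give no expected response rate. The interval method can be checked on the sensitivity example in Section 10.0: the Clopper-Pearson interval for 22/26 is 65.1% to 95.6%, as stated there (65% to 96%). The remaining rows of Tables 12 and 13 also reproduce to rounding.

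**Direction, without assumptions.** Every subject whose response is confirmed also has at least one scan that meets the criterion. Confirmed responders are thus a subset of single-scan responders, and the single-scan rate is equal or higher.

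**Number of chances.** Radiation lasts 6 weeks. Clinical MRI follows 4 weeks after it ends and then every 9 weeks (Section 6.0), so at about weeks 10, 19, 28 and so on from the start of radiation. Three scans reach week 28, six reach week 55, and there are up to 11 by week 104.

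**Size, as an illustration for PR only.** The documents give no measurement error, so the following are assumptions: a constant true ratio R of follow-up to baseline size, and independent lognormal error on the baseline and on each follow-up scan, with s = √ln(1 + CV²). Scan k is scored PR if R·exp(e_k − e_0) ≤ 0.5. For one scan the probability is Φ[ln(0.5/R)/(s√2)]. With R = 0.6 and CV 15%, s = 0.149 and ln(0.5/0.6) = −0.182, giving Φ(−0.86) = 19%. For several scans, simulation compares any one scan with any two consecutive scans:

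| True shrinkage | CV | Scans | PR on any one scan | PR on two consecutive scans |
|---|---|---|---|---|
| 40% (not a PR) | 15% | 3 | 38% | 12% |
| 40% | 15% | 6 | 51% | 21% |
| 40% | 10% | 3 | 22% | 5% |
| 40% | 10% | 6 | 32% | 9% |
| 40% | 5% | 6 | 2% | 0.2% |
| 30% (not a PR) | 15% | 6 | 20% | 4% |
| 20% (not a PR) | 15% | 6 | 6% | 1% |
| 55% (true PR) | 15% | 3 | 89% | 63% |
| 60% (true PR) | 15% | 3 | 97% | 83% |
| 60% | 15% | 6 | 99% | 94% |

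The effect is concentrated in lesions just short of the 50% threshold. At CVs up to 15%, the excess for a true shrinkage of 20% or less stays under 6 percentage points. It grows with larger error: at 20% CV and 3 scans, a true 20% shrinkage gives 11.1% against 1.8%.

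**In subjects.** This needs a further assumption, a distribution of true ratios. With median 0.9 and log-SD 0.5 (true PR rate 12.0%) and 3 scans, the single-scan rates at CV 10%, 20% and 30% are 16.5%, 22.5% and 29.2%, against confirmed rates of 11.7%, 12.5% and 14.2%. The differences are about 2.1, 4.3 and 6.4 of 43 subjects (for example 0.048 × 43 = 2.1). Over medians of 0.8 to 1.0 and 3 or 5 scans, the range was 1.3 to 7.5 of 43.

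**The case against.** Several points on the other side stand.

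- Section 8.1 is silent on confirmation; it does not say that one scan suffices. Nor does any section set out how best response is picked from the series of scans. Taking the most favourable scan is the usual meaning, but it is an inference.
- Confirming progression but not response is not in itself inconsistent. The repeat scan for progression serves to separate pseudoprogression, a reason that does not apply to response.
- The illustration rests on assumed error, constant size and independence. Multiplicative error never brings a lesion to zero, so it says nothing about CR. A steroid or bevacizumab effect may also persist over two scans, in which case confirmation would not remove it.
- Confirmation has its own downward bias: it loses true responses when scans are few.
- The endpoint is secondary and descriptive. The primary sensitivity and specificity analysis is untouched, and the protocol does not say that the larger study will be powered on response rate.

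A reader might also infer that a subject whose CR was reached through the residual-abnormality route, judged off therapy, can never qualify for retreatment, because 7.11 asks for at least two pembrolizumab treatments after the initial CR. The text does not support that. The requirement belongs only to the first of two alternative routes; the second, for stopping after 24 months with CR, requires no treatments after the CR. Section 7.11 also turns on systemic progression with CR maintained in the brain, which has little bearing on the GBM subjects. What remains is a tension between 8.1 and the first route.

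**Conclusion.** The point holds as a gap in definition and reporting, of minor weight. As written, one scan can meet CR or PR, confirmed CR has no definition, and the reported response rate can only equal or exceed a confirmed one. It may be overstated; the documents do not show that it is, or by how much. In the illustration, lesions truly at 60% of baseline are scored PR in 22% to 51% of cases on a single scan, against 5% to 21% with confirmation, at CVs of 10% to 15% and 3 to 6 scans. The excess shrinks to about 2 points at 5% CV. These figures depend on the stated assumptions and concern PR alone; a claim that the CR rate is inflated has no calculation behind it.

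**What to change.** For the analysis only: state in Sections 8.1 and 10.0 how best response is selected, and report two categories separately, each with an exact 95% interval. Confirmed CR/PR would mean that the criterion is still met on the next scheduled clinical MRI, at least 4 weeks later; unconfirmed CR/PR would be all others that met it. Say that these are reporting categories and do not govern treatment.

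The cost is wording, since the 9-weekly scans already exist. The confirmed rate will be lower. It will miss true responses when scans are few (at 15% CV and 3 scans, a true 55% shrinkage falls from 89% to 63%) and any response first seen on the last scan. Showing both categories keeps that information.

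Separately, the sponsor should reconcile the use of confirmed CR in 5.4.2 and 7.11, and the off-therapy wording in 8.1 with the first route in 7.11. No clinical rule is proposed here.
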